12. STUDY POPULATION

Each patient who signs an informed consent and meets Entry Criteria or Inclusion/Exclusion Criteria will be enrolled in the study. Patients will receive study product in an open-label fashion (see instructions in [Section 13.4](#)) for entire trial period (i.e., the treatment assignment, E-BPO, 5% Cream (Encapsulated Benzoyl Peroxide Cream, 5%, S5G4T-1), will be known to the patient, to study personnel, Sol-Gel personnel and its representatives.

12.1. Entry Criteria (only applies for patients entering from Phase 3, SGT-54-01 or SGT-54-02)

To be included in the study, patients must meet the following eligibility /inclusion criteria:

1. Patient must sign an Institutional Review Board (IRB) approved written informed consent for the extension study.
2. Complete 12-week or within the week 12 window time (± 4 days) of the double-blind treatment period of study SGT-54-01 or Study SGT-54-02 and missed not more than one visit of Visits 3, 4 or 5 in Study SGT-54-01 or Study SGT-54-02.
3. Patients who in the opinion of the investigator, are likely to be able to follow the restrictions of the protocol and complete the study.

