18.4. Safety Evaluation

Safety will be evaluated by tabulations of adverse events (AEs), Cutaneous Safety Assessments for dryness and scaling, Local Tolerability Assessment for itching and burning and assessments for erythema and telangiectasia will be presented with descriptive statistics at Baseline and at the scheduled study visits. Frequencies and percentages for each outcome category will be included in these statistics. Safety data will be presented for patients in the Safety Population with tabulations for the following periods 12 to 28 weeks, > 28 to 52 weeks and > 52 weeks to the end of the study, as well as an overall for all periods.

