6. STUDY DESIGN

6.1 Overall Study Design

Approximately 700 patients will be enrolled at up to 56 sites. All patients in this open-label, long-term safety study will be assigned to treatment with S5G4T-1.

The objective of this study is to determine the long-term safety and tolerability of daily use of S5G4T-1 in papulopustular rosacea patients.

Patients who successfully completed the 12-week treatment period from Study SGT-54-01 or Study SGT-54-02 may be offered to continue in the long-term safety, open-label extension study (Study SGT-54-07) for up to an additional 40 weeks (sum of up to 52 weeks). The Sponsor may terminate the study once 300 patients complete a total of 28 weeks of treatment and 100 patients complete a total of 52 weeks.

Patients who completed the 12-week treatment period (± 4 days) for SGT-54-01 or SGT-54-02 and did not miss more than one visit (Visit 3, 4 or 5) in SGT-54-01 or SGT-54-02 will be admitted into the 54-07 study after the Entry Criteria have been met and an ICF has been signed. Qualified patients will receive study product at Baseline and will be treated for up to 40 weeks. At each visit, the patients will be assessed for a 5-point scale IGA of rosacea. If a patient is assessed as “clear” (0) or “almost clear” (1), the patient will not be dispensed the study product. If a patient is assessed as “mild”, “moderate” or “severe” (score of 2, 3 or 4, respectively), study product will be dispensed and the patient will use the study product daily according to patient instructions. Rosacea Quality of Life Questionnaire (RosaQoL) will be completed at Baseline, Visits 5, 8, 11, and 14 and at End of Study or at early termination. The RosaQoL data of patients who were enrolled from SGT-54-01 or SGT-54-02, will be used from the questionnaire completed at Visit 6/Week 12 of SGT-54-01 or SGT-54-02. Rosacea erythema severity and telangiectasia assessments will be completed at all study visits. At each visit, the following safety measures will be recorded: monitoring for any local and systemic AEs, cutaneous safety (dryness, and scaling) and local tolerability (itching and burning/stinging) assessments on a scale ranging from 0 (None) to 3 (Severe), vital signs and physical examinations.

A urine pregnancy test is required at all visits for all females of child-bearing potential.

Clinical Evaluations will be performed at:

1. Visit 1/Screening, only applies for new patients

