8.1.3 Visit Windowing

For subjects receiving S5G4T-1 in 54-01/54-02, data from 54-01/54-02 will be included in summaries of 54-07. For subjects receiving vehicle in 54-01/54-02, baseline values will be sourced from 54-01/54-02 and data from follow-up visits of 54-07 will be used in summaries. The table below details the analysis visits to be summarized and the associated visits from 54-01/54-02 or 54-07 which will be sourced for each type of subject.

Analysis Visits for Efficacy and Safety Assessments

Analysis Visit	Subjects Receiving S5G4T-1 in 54-01/54-02	Subjects Receiving vehicle in 54-01/54-02
Week 4	54-01/02 - Week 4	54-07 - Week 4
Week 8	54-01/02 - Week 8	54-07 - Week 8
Week 12	54-01/02 - Week 12	54-07 - Week 12
Week 16	54-07 - Week 4	54-07 - Week 16
Week 20	54-07 - Week 8	54-07 - Week 20
Week 24	54-07 - Week 12	54-07 - Week 24
Week 28	54-07 - Week 16	54-07 - Week 28
Week 32	54-07 - Week 20	54-07 - Week 32
Week 36	54-07 - Week 24	54-07 - Week 36
Week 40	54-07 - Week 28	54-07 - Week 40
Week 44	54-07 - Week 32	Not available
Week 48	54-07 - Week 36	Not available
Week 52	54-07 - Week 40	Not available

Data from 54-07 will be mapped to the appropriate analysis visit described above based on nominal visit indications. Data from Early Termination (ET) and unscheduled visits will be determined using analysis visit windows. The analysis visit windows for ET and unscheduled visits are presented in the following table.

SGT-54-07 Analysis Visit Windows for Efficacy and Safety Assessments

Nominal Visit	Target Study Day¹	Window (Days)
Week 4	29	22 to 42
Week 8	57	43 to 70
Week 12	85	71 to 98
Week 16	113	99 to 126
Week 20	141	127 to 154
Week 24	169	155 to 182
Week 28	197	183 to 210
Week 32	225	211 to 238
Week 36	253	239 to 266
Week 40	281	267 to 294
Week 44	309	295 to 322
Week 48	337	323 to 350
Week 52	365	351 to 378

¹ Number of days since nominal Baseline visit of 54-07

Data collected at ET and unscheduled visits prior to study day 22 will not be analyzed. Data collected at ET and unscheduled visits after study day 378 will not be included in analyses.

The definition for the study day included in each study window is defined as below:

Study Day prior to Day 1 = Visit Date – Day 1 Date

Study Day on or after Day 1 = Visit Date – Day 1 Date + 1

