8.9.2 Adverse Events

AEs from 54-01/02 will be included in the analysis for 54-07. All AEs that were reported as ongoing in 54-01/02 will be added into the CRF for 54-07, while AEs reported as recovered/resolved will be pulled forward programmatically into 54-07.

AEs occurring during the study will be recorded and classified on the basis of MedDRA terminology. Descriptions of AEs will include the date of onset, the date the AE ended, the severity of the AE, the relationship to study product, the action taken regarding study product usage, the action taken to treat the AE, and the outcome. All reported treatment-emergent AEs (TEAEs) will be summarized by the number of patients reporting AEs, system organ class, severity, seriousness, and relationship to study product. TEAEs are those AEs with an onset on or after the date of the first study product application. For AEs recorded in the 54-07 study if the AE is not indicated as prior to first application on the CRF then it will be considered a TEAE. AEs from 54-01/02 for subjects who received S5G4T-1 in 54-01 or 54-02 will be considered a TEAE if they were considered at TEAE in the 54-01/02 study. AEs (including ongoing) from 54-01/02 study for subjects who received vehicle in 54-01 or 54-02 will be considered pre-treatment.

AEs will be summarized by period (and total) and by severity. Each patient will be counted only once within a SOC or a Preferred Term by using the AEs with the highest severity within each category.

AEs will be summarized by period (and total) and by relationship to study product. Each patient will be counted only once within a system organ class or a preferred term by using the AEs with the greatest relationship within each category.

If relationship to study drug is reported as definitely, probably, or possible, then this is defined as related. If relationship to study drug is reported as unlikely or not related, then this is defined as unrelated.

TEAEs will be summarized in total as well as by the following periods based on time of onset in relation to date of first application of S5G4T-1, based on the definitions below. Start dates will be imputed as described in Section 8.1.5.2.

- 0-12 Weeks $0 \leq \text{onset day} \leq 85$
- >12-28 Weeks $86 \leq \text{onset day} \leq 197$
- >28-52 Weeks $198 \leq \text{onset day} \leq 365$
- >52 Weeks $\text{onset day} \geq 366$

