^a Counts reflect numbers of subjects reporting one or more adverse events that map to MedDRA. At each level of summarization (System Organ Class or Preferred Term) subjects are counted once under the greatest reported relationship.

Note: MedDRA Version 21.0.

Treatment-emergent adverse events are those events with an onset after the first application of E-BPO 5% Cream.

Related defined as “Definitely”, “Probably”, or “Possible”. Not Related defined as “Unlikely” or “Not related”.

SOURCE: USERNAME\SPONSOR\PROJECT\JOBNAME (DATE, TIME)

Table 14.3.1.3.1: Summary of Treatment-Emergent Adverse Event Characteristics - By Period
(Safety Population)
(Page 1 of 2)

	0-12 Weeks (N=xxx)	>12-28 Weeks (N=xxx)	>28-52 Weeks (N=xxx)	>52 Weeks (N=xxx)
Subjects Reporting Any Treatment-Emergent Adverse Event	xx (xx.x%)	xx (xx.x%)	xx (xx.x%)	xx (xx.x%)
Number of Treatment-Emergent Adverse Events	xx	xx	xx	xx
Subjects Reporting Any Serious Treatment-Emergent Adverse Event	xx (xx.x%)	xx (xx.x%)	xx (xx.x%)	xx (xx.x%)
Number of Serious Treatment-Emergent Adverse Events	xx	xx	xx	xx
Subjects Reporting Treatment-Emergent Adverse Event with Outcome of Fatal	xx (xx.x%)	xx (xx.x%)	xx (xx.x%)	xx (xx.x%)
Number of Treatment-Emergent Adverse Events with Outcome of Fatal	xx	xx	xx	xx
Subjects Who Discontinued Study Drug Due to a Treatment-Emergent Adverse Event	xx (xx.x%)	xx (xx.x%)	xx (xx.x%)	xx (xx.x%)
Number of Treatment-Emergent Adverse Events Leading to Discontinuation of Study Drug	xx	xx	xx	xx
Subjects Who Discontinued from the Study Due to a Treatment-Emergent Adverse Event	xx (xx.x%)	xx (xx.x%)	xx (xx.x%)	xx (xx.x%)
Number of Treatment-Emergent Adverse Events Leading to Discontinuation of Study	xx	xx	xx	xx

Note: Treatment-emergent adverse events are those events with an onset after the first application of E-BPO 5% Cream.

Related defined as “Definitely”, “Probably”, or “Possible”. Not Related defined as “Unlikely” or “Not related”.

Periods defined from date of first dose of E-BPO 5% Cream. Period >52 Weeks includes all adverse events reported after week 52 through the end of study participation.

By subject denominator for each period includes the number of subjects in the safety population completing the period or experiencing an adverse event during the period.

SOURCE: USERNAME/SPONSOR/PROJECT/JOBNAME (DATE, TIME)

Table 14.3.1.3.1: Summary of Treatment-Emergent Adverse Event Characteristics – By Period
(Safety Population)
(Page 2 of 2)

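### The pooled 0-12 week and overall TEAE tables mix prior-S5G4T-1 rollovers, who had to complete 12 weeks to enter, with prior-vehicle rollovers who could stop early, and so understate early AE discontinuation

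*SAP*

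**What the plan says.** *Entry.* Protocol 12.1 sets the condition "Complete 12-week or within the week 12 window time" (±4 days), with at most one of Visits 3 to 5 missed. SAP 6.1 repeats that patients who finished the 12 weeks and "did not miss more than one visit (Visit 3, 4 or 5) in SGT-54-01 or SGT-54-02 will be admitted". SAP section 10 adds that enrolment was already complete and that every enrolled subject had completed 54-01 or 54-02.

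*Adverse events.* SAP 8.9.2 states that "AEs from 54-01/02 will be included in the analysis for 54-07". Under the same section, "AEs from 54-01/02 for subjects who received S5G4T-1 in 54-01 or 54-02 will be considered a TEAE" if they were so classed in the parent trial, whereas parent-trial AEs "for subjects who received vehicle in 54-01 or 54-02 will be considered pre-treatment". TEAEs are tabulated in total and by day of onset after first S5G4T-1 application: 0-12 weeks (to day 85), >12-28, >28-52 and >52 weeks. Protocol 18.4 instead asks for "tabulations for the following periods 12 to 28 weeks, > 28 to 52 weeks and > 52 weeks to the end of the study", plus an overall summary. SAP section 10 does not mention the extra period.

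*Visit data.* SAP 8.1.3 says that for S5G4T-1 recipients "data from 54-01/54-02 will be included in summaries of 54-07", so their Week 4, 8 and 12 tolerability scores come from the parent trial.

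*Tables.* Tables 14.3.1.2.1 (overall) and 14.3.1.3.1 (by period) have the row "Subjects Who Discontinued Study Drug Due to a Treatment-Emergent Adverse Event", a matching row for leaving the study, and rows for maximum severity, alone and within relationship. The overall TEAE shells have one E-BPO column and the by-period shells have four period columns. Neither is divided by parent arm. The by-period denominator is the Safety Population subjects who complete the period or have an AE in it.

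**The concern.** A patient who started S5G4T-1 in a parent trial and left before Week 12 because of a reaction cannot appear in 54-07. The patients who do appear bring their parent-trial weeks 0-12 with them, as numerator events and as denominator. The column in which a reader would look for early intolerance is therefore filled partly by patients selected for having stayed through that period.

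The study's objective is the nature, severity and frequency of AEs. A 0-12 week column read next to the >12-28 week column would make the early phase look safer than it is for someone starting the product. The overall discontinuation percentage has the same gap. Neither document describes this selection as a limitation, and no table or sensitivity summary is planned that would correct it.

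**Working it through.** The plan states no event rate on this point, so there is no figure to reproduce. The structural part uses document inputs. The illustration needs assumed ones.

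**1. What each cohort contributes to weeks 0-12**

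| | Prior S5G4T-1 | Prior vehicle |
|---|---|---|
| Where weeks 0-12 on S5G4T-1 take place | 54-01/54-02 | 54-07 |
| Can leave in that window and still be counted | Only after the parent Week 12 visit | Yes |
| Parent-trial AEs | TEAEs | Pre-treatment |
| In the 0-12 week denominator | Practically all | Period completers and anyone with an AE |

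**2. Days at risk of study discontinuation, prior-S5G4T-1 cohort**

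Inputs: parent Week 12 is Day 85 (Protocol section 11), the window is ±4 days (Protocol 12.1), and the period ends on day 85 (SAP 8.9.2). Day 1 of the parent trial is taken as the day of first application. At-risk days = max(0, 85 − completion day + 1).

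- Completion on day 81: 85 − 81 + 1 = 5 days, 5/85 = 5.9%.
- Completion on day 85: 1 day, 1/85 = 1.2%.
- Completion on day 89: 0 days.

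So 80 to 85 of the 85 days (94% to 100%) are free of study discontinuation by design.

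**3. Why near zero and not zero**

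- Periods follow AE onset. An AE that began in parent weeks 0-12, was ongoing at rollover and led to withdrawal in 54-07 falls in the 0-12 week column.
- A patient completing on days 81 to 84 has a few at-risk days left.
- Entry does not expressly bar someone who stopped the product but still attended Week 12.

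**4. Illustration for the 0-12 week rate**

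Let f be the prior-S5G4T-1 share of the Safety Population, d the AE-discontinuation rate over the first 12 weeks after starting S5G4T-1, and e the small rate that the prior-S5G4T-1 cohort still contributes. None of these is in the documents.

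Displayed rate ≈ (1 − f) × d + f × e.

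With e = 0:

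| d | f = 0.50 | f = 0.67 |
|---|---|---|
| 3% | 0.50 × 3% = 1.5% | 0.33 × 3% = 1.0% |
| 5% | 0.50 × 5% = 2.5% | 0.33 × 5% ≈ 1.7% |

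In counts, with the planned enrolment of about 700, f = 2/3 and d = 3%: 700 × 1/3 × 0.03 = 7 shown, against 700 × 0.03 = 21 if all had been at risk.

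Two features make the shrinkage smaller than this. Any e above zero raises the displayed rate. Prior-vehicle subjects who leave in weeks 0-12 without an AE also drop out of the denominator. If they are a fraction q of that cohort, the factor becomes (1 − f)/(1 − (1 − f)q), which exceeds 1 − f. A half to a third is therefore a limiting case.

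**5. Overall tables**

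The overall discontinuation rows lack the same early events. How much this lowers them depends on what fraction of AE discontinuation is early, so only the direction can be given.

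**6. Severe related reactions**

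Protocol 16.7 discontinues a patient with a severe product-related AE. If the parent trials had a similar rule, which the documents do not show, severe related events would be largely missing from this cohort's weeks 0-12. SAP section 4 shows that such events occur: in the 12-week Phase 2 study, 5% E-BPO was withdrawn from one subject for a severe application site reaction. The arm size is not given.

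**The case against.** The best defence is that cumulative counting is the protocol's own design. Its exposure targets include the 12 double-blind weeks, Protocol 18.2 counts parent-trial dosing towards the Safety Population, and Protocol 18.4 asks for an overall summary. Without a 0-12 week column, the prior-vehicle patients' first 12 weeks on drug would appear in no period. SAP section 2 gives the SAP precedence where the two differ, and the study is descriptive, with no decision rule tied to this column. All of that stands. It justifies including the parent data and adding the period, but not pooling without a split or a warning.

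Much is also shown elsewhere. Table 14.0.1 gives 54-07 discontinuation reasons by parent arm, and Table 14.3.1.1 gives tolerability by parent arm at each visit. Listings 16.2.7.2.5 and 16.1.7 together identify each AE discontinuation, its onset day and the prior treatment. SAP 8.1 promises a parent-arm presentation where applicable. A reader might infer that the tolerability summaries can be read only as a pooled figure. They cannot be faulted on that ground, and they need only a footnote. The TEAE shells, however, do not carry the split, and no output restores the parent-trial drop-outs.

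Prior-vehicle patients are not a clean reference either. They completed a vehicle course, and product is withheld at 54-07 visits with IGA 0 or 1 (Protocol 14.1), so their weeks 0-12 can include untreated time. This limits what their column can be called, but they were not selected for tolerating S5G4T-1.

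**Conclusion.** The point holds as a reporting bias with a known direction and unknown size. In the prior-S5G4T-1 cohort, AE-related discontinuation in weeks 0-12 is near zero by design. Pooling therefore lowers the 0-12 week and overall discontinuation rows, and probably the early severe related rows. The severe-reaction part rests on the unverified assumption that the parent trials withdrew such patients. The bias in drug discontinuation, as distinct from study discontinuation, rests on parent completion meaning that patients stayed on product.

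Two stronger readings are tempting, and the documents do not support them. The first is that the 0-12 week discontinuation rows are structurally zero for this cohort. Assignment by onset, with ongoing parent AEs re-entered in the 54-07 CRF, leaves a route for real events. The second is that the reported rate equals a computable fraction of the true rate. The share and the true rate are both absent, and the stated denominator changes the factor, so a half to a third for a share of 0.50 to 0.67 is illustration only. The missing entry in SAP section 10 is a documentation gap, not a breach of the protocol.

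**What to change.** - In SAP 8.9.2 and the AE shells 14.3.1.2.x to 14.3.1.5.x (TEAE and serious TEAE, overall and by period), add the prior-vehicle and prior-S5G4T-1 columns already used in Tables 14.0.1, 14.3.0.1 and 14.3.1.1, and keep the pooled column.
- Show the actual counts for prior-S5G4T-1 subjects in the 0-12 week discontinuation rows. Printing NA would hide withdrawals caused by early-onset AEs.
- Footnote the prior-S5G4T-1 0-12 week and overall AE rows, and their Week 4 to 12 tolerability rows, as conditional on completing the 12-week parent period.
- Use the prior-vehicle column as the main description of early AE discontinuation after starting S5G4T-1, and note that these subjects are completers of vehicle treatment.
- List the added 0-12 week period in SAP section 10.

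The cost is SAP wording, footnotes and a column split that already exists in other shells. The by-period tables become wider or need a page per arm. No new data are needed. The early figures will rest on fewer patients and may look less favourable.

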8. OBJECTIVE

The objective of this long-term safety study is to determine the nature, severity and frequency of the AE rate, the Cutaneous Safety Assessment and the Local Tolerability Assessment of S5G4T-1 when applied once daily, if applicable, for up to 52 weeks

The safety endpoints to be assessed include the following:

- The frequency of both local and systemic adverse events
- Investigator Cutaneous Safety Assessment (dryness and scaling) and Local Tolerability Assessment (itching and burning/stinging) at Baseline and at all study visits.

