xxxxxx	xxxx	xxxxxxxxxx	xxxxxxxxxxxxxxxxxx	xxxxxxxxxx	xxxxxx xxxxx
xxxxxx	xxxx	xxxxxxxxxx	xxxxxxxxxxxxxxxxxx	xxxxxxxxxx	xxxxxx xxxxx
xxxxxx	xxxx	xxxxxxxxxx	xxxxxxxxxxxxxxxxxx	xxxxxxxxxx	xxxxxx xxxxx
xxxxxx	xxxx	xxxxxxxxxx	xxxxxxxxxxxxxxxxxx	xxxxxxxxxx	xxxxxx xxxxx

SOURCE: USERNAME\SPONSOR\PROJECT\JOBNAME (DATE, TIME)

Listing sorted by Subject.

Listing 16.2.1.1: End of Study Information
(Page xx of yy)

Subject	Age/Sex	Eval	Date of First Application	Date of Last Application	Date of Study Completion/Discontinuation (Day) ¹	Did Subject Complete the Study	Primary Reason for Study Discontinuation
xxxxxx	xxxx	xxxxxxxx	xxxxxxxxxx	xxxxxxxxxx	xxxxxxxxxxxxxxxx	xxx	
xxxxxx	xxxx	xxxxxxxx	xxxxxxxxxx	xxxxxxxxxx	xxxxxxxxxxxxxxxx	xx	xxxxxx xxxxx
xxxxxx	xxxx	xxxxxxxx	xxxxxxxxxx	xxxxxxxxxx	xxxxxxxxxxxxxxxx	xx	xxxx xx xxxxxxxxxxx xxxxxxxxxxx xxx xx xxxxxxxxxxx xxxxx xxxxx xxxxx xxx xxxx

¹ Day is calculated as date - date of first application of E-BPO 5% Cream (from SGT-54-01/SGT-54-02 or SGT-54-07) for dates prior to first application. Otherwise, day is calculated as date - date of first application + 1 for dates on or after first application.

SOURCE: USERNAME\SPONSOR\PROJECT\JOBNAME (DATE, TIME)

Listing sorted by Subject.

If Primary Reason for Study Discontinuation is Lost to Follow-Up, Protocol Violation, Withdrawal by Subject, or Other, the reason specification will be included following a colon (for example, WITHDRAWAL BY SUBJECT: xxxxx)

Listing 16.2.2.1: Inclusion/Exclusion Criteria
 (Page xx of yy)

Subject	Age/Sex	Eval	Criterion Failed	Description
xxxxxx	xxxx	xxxxxxxxxx	xxxxxx	xxxxx xxx xx xxxxxxxx xxxx xxxxxxxxxxxxxxxxxxxxxxxx xxxxxxxx
xxxxxx	xxxx	xxxxxxxxxx	xxxxxx	xxxxx xxx xx xxxxxxxx xxxx xxxxxxxxxxxxxxxxxxxxxxxx xxxxxxxx
xxxxxx	xxxx	xxxxxxxxxx	xxxxxx	xxxxx xxx xx xxxxxxxx xxxx xxxxxxxxxxxxxxxxxxxxxxxx xxxxxxxx
			xxxxxx	xxxxx xxx xx xxxxxxxx xxxx xxxxxxxxxxxxxxxxxxxxxxxx xxxxxxxx
			xxxxxx	xxxxx xxx xx xxxxxxxx xxxx xxxxxxxxxxxxxxxxxxxxxxxx xxxxxxxx xxxxxxxxxxxxxxxxxxxx xxxxxxxxx x xxxxxxxxxxxxxxxxxxxx xxx

SOURCE: USERNAME\SPONSOR\PROJECT\JOBNAME (DATE, TIME)

Listing sorted by Subject and Criterion Failed.

Listing 16.2.2.2: Screen Failure
 (Page xx of yy)

Subject	Age/Sex	Eval	Date of Screen Failure	Reason for Screen Failure
xxxxxx	xxxx	xxxxxxxxxx	xxxxxxxxxx	xxxxx xxx xx xxxxxxxx xxxx xxxxxxxxxxxxxxxxxxxxxxxx xxxxxxxx
xxxxxx	xxxx	xxxxxxxxxx	xxxxxxxxxx	xxxxx xxx xx xxxxxxxx xxxx xxxxxxxxxxxxxxxxxxxxxxxx xxxxxxxx

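### The three bounded AE period columns last 85, 112 and 168 days and carry no person-time, so a constant AE hazard would print as a rising percentage across them

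*SAP*

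**What the plan says.** SAP 8.9.2: "TEAEs will be summarized in total as well as by the following periods based on time of onset". The limits are onset days 0 to 85, 86 to 197, 198 to 365, and 366 onward. Protocol 18.4 already fixes the later cuts, asking for "tabulations for the following periods 12 to 28 weeks, > 28 to 52 weeks and > 52 weeks to the end of the study"; the SAP adds the 0-12 week column. Onset is counted from first S5G4T-1 application, in the Phase 3 study or in 54-07. The footnotes to the listings define the day: "Otherwise, day is calculated as date - date of first application + 1 for dates on or after first application".

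The by-period shells (Tables 14.3.1.3.1 to 14.3.1.3.4, and 14.3.1.5.1 to 14.3.1.5.4 for SAEs) print n (%) of subjects. The two characteristics tables add counts of events. The footnoted denominator is a head count: patients who complete the period plus those who have an AE in it. On the last column the footnote says: "Period >52 Weeks includes all adverse events reported after week 52 through the end of study participation".

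Exposure (SAP 8.9.1, Table 14.3.0.1) is summarised over the whole study only, and is not calculated for patients lost to follow-up or with incomplete dosing records. Neither document plans person-time by AE period or an exposure-adjusted rate. Protocol section 8 words the objective as "to determine the nature, severity and frequency of the AE rate", together with the cutaneous and tolerability assessments.

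**The concern.** Columns ordered by time since first application invite the reader to ask whether AEs become more or less common with longer use. A percentage of patients answers that only if the columns are equally long, and here the third is about twice the first. This is a separate matter from who is in the denominator: with every patient fully followed, a longer window still collects more events. Two misreadings are possible. A steady hazard could be taken for cumulative toxicity, or a hazard that truly declines could be taken for a flat one. The reader cannot convert the columns to rates, because no days at risk are reported by period.

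The overall tables have a milder form of the problem. Their single E-BPO column pools prior-vehicle patients, whose S5G4T-1 follow-up ends at about Week 40, with prior-S5G4T-1 patients followed to about Week 52 (SAP 8.1.3).

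**Working it through.** **Inputs.** Period limits are from SAP 8.9.2. The first application is Day 1 and there is no Day 0, so the first column is 85 days (86 only if the printed 0 were a real day). The AE hazard is an assumption; the documents give none.

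**Cut-offs reproduced.** 7 × weeks + 1 for 12, 28 and 52 weeks gives 85, 197 and 365, as in the SAP.

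**Lengths.** 85; 197 − 86 + 1 = 112; 365 − 198 + 1 = 168. Ratios to the first: 112/85 = 1.32 and 168/85 = 1.98. Expected raw event counts under a constant hazard and complete follow-up rise in the same ratios.

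**Percentages under a constant hazard, complete follow-up.** Let p0 be the first-column percentage. Then λ = −ln(1 − p0)/85 and column percentage = 1 − exp(−λ × days). For p0 = 10%, λ = 0.10536/85 = 0.0012395 per day, so 1 − exp(−0.1388) = 13.0% and 1 − exp(−0.2082) = 18.8%.

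| p0 | 0-12 wk | >12-28 wk | >28-52 wk | Third/first |
|---|---|---|---|---|
| 2% | 2.0% | 2.6% | 3.9% | 1.96 |
| 5% | 5.0% | 6.5% | 9.6% | 1.93 |
| 10% | 10.0% | 13.0% | 18.8% | 1.88 |
| 20% | 20.0% | 25.5% | 35.7% | 1.78 |
| 40% | 40.0% | 49.0% | 63.6% | 1.59 |

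**Converse.** For rare events the columns look flat if the hazard falls to 85/112 = 0.76 and then 85/168 = 0.51 of its first-period value.

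**With the SAP denominator.** Prior-vehicle patients stop at about Day 281, so they cannot complete the third period and enter its denominator only if they have an AE. Take dropout hazard μ and a share s of patients entering a period with t days available. AE patients = s × λ/(λ + μ) × (1 − exp(−(λ + μ)t)). AE-free completers = s × exp(−(λ + μ)t), or zero if that group cannot reach the period end. Printed percentage = AE patients/(AE patients + completers). Assuming one third prior vehicle and 20% dropout by Day 281, p0 = 5% gives 5.2/6.8/12.6% and p0 = 20% gives 20.6/26.4/43.4%. Over dropout of 0 to 40% and a prior-vehicle share of 0 to 50%, the third column at p0 = 5% runs from 9.6% to 16.2%.

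**Fourth column.** On nominal windows a prior-S5G4T-1 patient reaches at most Day (85 + 4) + (281 + 10) − 1 = 379, which is 14 days past Day 365. At p0 = 5%, with everyone at risk as the denominator, that is 0.8%. Even 44 days (14 plus 30 after the end of treatment) would give 2.6%.

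**Overall tables.** At p0 = 10% the cumulative percentage is 1 − exp(−0.0012395 × 281) = 29.4% by Day 281 and 1 − exp(−0.0012395 × 365) = 36.4% by Day 365. The pooled figure lies between these and depends on the mix of the two groups.

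**Rate instead.** Events per 100 patient-years = λ × 36,525, and column length cancels. The result is the same in all three columns: 22.0 at p0 = 5%, 45.3 at 10% and 95.9 at 20%. At p0 = 5% and 20% this was unchanged under every dropout and prior-vehicle setting above.

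**The case against.** The study is single-arm and descriptive, the column headings show the weeks, and neither document says that the periods exist to compare risk over time. The 28- and 52-week cuts match the exposure milestones of 300 and 100 patients. The safety endpoint is worded as frequency, which percentages and counts can satisfy. Local irritation, the expected problem, is scored at 4-week visits and mostly kept out of the AE data. All of this is fair, and it is why the matter is one of presentation. But a rate is also descriptive, headings do not supply days at risk, and the tolerability tables say nothing about other AEs.

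Some stronger readings are not supported:

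- A reader might infer a rise across all four columns. The last is a remnant of about two weeks, and completing an open-ended period is undefined.
- A reader might take 18.8% as a forecast. It assumes complete follow-up, which prior-vehicle patients cannot have, and the printed values also depend on dropout and the denominator rule.
- A reader might infer that the objective, because it mentions a rate, requires a person-time analysis. The wording does not go that far.

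Two objections limit any remedy. Product is withheld at IGA 0 or 1, so time since first application includes off-treatment days. Selection also remains: rollover patients had to complete the 12-week Phase 3 treatment period, and patients with a severe related AE are discontinued. A rate corrects for column length, not for these.

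**Conclusion.** The point holds for the three bounded columns. Their lengths are in the ratio 1 : 1.32 : 1.98, and the plan provides nothing with which to adjust for it. At a constant hazard and complete follow-up the third column prints 1.6 to 2.0 times the first for p0 between 40% and 2%. The direction holds at any constant hazard; the size depends on the assumed p0. The SAP denominator does not offset the effect and, in the settings tried, either left it unchanged or added to it. Imputing completely missing AE start dates to the first dose date works slightly the other way, by adding events to the first column. No planned test is affected, because there is none. The addition is cheap and worth making, since safety over duration of use is what the study describes.

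**What to change.** Before database lock, amend SAP 8.9.2 and the characteristics tables: 14.3.1.2.1 and 14.3.1.3.1, and the SAE versions 14.3.1.4.1 (a number also given to the vital signs table) and 14.3.1.5.1. Add two rows, for each period and overall: total patient-years at risk, and TEAEs per 100 patient-years.

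- Person-time: every Safety Population patient contributes days from the later of period start or first S5G4T-1 application to the earlier of period end or last contact. Do not substitute the SAP 8.9.1 exposure variable, which is missing for patients lost to follow-up.
- If a rate of patients with an event is also shown, define it as the first event within the period and stop that patient's time at the event. Without stopping, a constant hazard at p0 = 10% gives a false decline of 43.0/42.3/40.9 per 100 patient-years (for example, 0.100/(85/365.25) × 100 = 43.0).
- Label the rates as time since first application, including instructed off-treatment days.
- Base any comparison of periods on the rates, and keep the percentages.

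Rates by system organ class and preferred term are optional. The cost is SAP wording, a few extra rows and one derived variable per period; first-application and study completion or discontinuation dates are already in Listing 16.2.1.1.
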